THIS DOCUMENT CONTAINS CONFIDENTIAL AND PROPRIETARY INFORMATION OF EDWARDS LIFESCIENCES, LLC. IT MAY NOT BE REPRODUCED OR DISCLOSED WITHOUT PRIOR WRITTEN PERMISSION FROM EDWARDS LIFESCIENCES, LLC.

Edwards Lifesciences, Edwards, the stylized E logo, HemoSphere, Acumen IQ, Swan Ganz and ForeSight Elite are trademarks of Edwards Lifesciences Corporation.

subjects, may be unblinded to the randomization assignment to set up the devices in the OR accordingly. However, the delegated coordinator/designee must not reveal the randomization assignment to clinician prior to start of the surgery.

A baseline Creatinine, NT pro-BNP and Troponin will be drawn on the day of procedure. Any fluids and vasoactive medications administered, intraoperative complications, and adverse events that occurred during the procedure will be collected.

After surgery on post-operation day 1 (or within 24 hours of extubation), any fluids and vasoactive medications, post-operative complications, and adverse events will be collected. Troponin will be drawn and an MMSE will be administered.

[figure not shown]
Before hospital discharge (generally post-operation day 2-7, but may vary), another MMSE will be administered. Troponin and NT pro-BNP will be drawn POD1, 2, 3. Creatinine will be drawn POD 1, 2, 3.

While the subject is in the ICU, an ICU-specific Confusion Assessment Method (CAM-ICU 7) will be administered twice daily. This assessment will be administered for up to 7 days post-operation in the ICU or until the subject is transferred to the hospital floor.

While the subject is located on the hospital floor, a Brief Confusion Assessment Method (bCAM) be administered twice daily. This assessment will be administered until post-operation day 7 or until hospital discharge (whichever comes first).

Additional information will be collected when the subject is discharged. A 30-day follow up will take place 30 days (± 15 days) post-operation, either by phone call or in-person. If the follow-up takes place in-person, an MMSE will be administered at that time.

Figure 4. Sample Timeline Diagram

THIS DOCUMENT CONTAINS CONFIDENTIAL AND PROPRIETARY INFORMATION OF EDWARDS LIFESCIENCES, LLC. IT MAY NOT BE REPRODUCED OR DISCLOSED WITHOUT PRIOR WRITTEN PERMISSION FROM EDWARDS LIFESCIENCES, LLC.
 Edwards Lifesciences, Edwards, the stylized E logo, HemoSphere, Acumen IQ, Swan Ganz and ForeSight Elite are trademarks of Edwards Lifesciences Corporation.

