7. STATISTICAL METHODS

Statistical Analysis Plan (SAP)

There will be a formal SAP, separate from this HPI CARE Trial protocol. The formal SAP will be completed prior to database lock and the analysis of any HPI CARE Trial endpoints data. The SAP will detail the planned statistical analyses. The subsections below summarize the planned analyses.

Primary Effectiveness Endpoint

The primary objective of this trial is to determine whether the use of the Acumen™ HPI Feature Software to guide hemodynamic management in critically ill patients in the cardiac operating room (OR) and the cardiovascular intensive care unit (CVICU) reduces the duration (t[mins]) of hypotension below a threshold of Mean Arterial Pressure (MAP), defined as MAP <65mmHg.

Sample Size Justification

In the HPI CARE Trial, the reduction of the mean duration of hypotension in the operating room (OR) and intensive care unit (ICU), is the primary endpoint. The following statistical hypotheses are designed and used for the sample size estimation.

$$H_n: \mu_1 \geq \mu_0$$

$$H_a: \mu_1 < \mu_0$$

where μ_1, μ_0 are the mean hypotension duration of the test arm and reference arm, respectively.

Because there are no publications available targeting hypotension management in the ICU, the sample size estimation is conducted based on the summary statistics from OR measurement. By the summary statistics (mean and standard deviation) of hypotension duration from post-CPB and closed chest ^[3,5], the following statistics are calculated and applied in sample size estimation: hypotension mean=29 (minutes), standard deviation=29.4 (minutes).

By clinical study design, type I error $\alpha = 0.025$ (one side test), test power= $(1 - \beta) = 0.80$, the expected hypotension duration reduction rate by HPI software and the treatment protocol is 30%, the expected ratio of hypotension duration standard deviation divided by the mean hypotension in the test arm will be 1.10 (obtained from a previous non-cardiac OR HPI study, Edwards Lifesciences), with SAS PROC POWER, the estimate of sample size is 171 per group. β is type II error.

Primary Safety Endpoint

The primary safety endpoint is to assess all serious intraoperative and post-operative adverse events through 30 days, including serious device-related events.

Analysis Populations

A. mITT population

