9. REPORTABLE EVENTS

Recording and Reporting of Adverse Events

The Investigator and/or Designee(s) will determine whether any adverse events (AEs) have occurred. An AE is defined as any untoward medical occurrence in a clinical trial of a Trial Device regardless of the causal relationship of the problem with the device or, if applicable, other trial treatment or diagnostic product(s). Information for AEs with the trial devices will be collected from the time a subject begins the trial related procedure and/or is exposed to trial product(s). AEs will also be collected during surgical intervention, post intervention, discharge and through the follow-up. AEs may be volunteered by subjects, clinicians, elicited from questioning by Investigator and/or Designee(s), or collected via observation. When a device- or trial-related AE is suspected all available event information and will be provided to the Medical Reviewer.

Once an AE/SAE/UAE is confirmed as such, event, date of onset, severity, duration, treatment (if required), resolution (or ongoing), assessment of seriousness, relationship to trial procedure and relationship to device will be recorded on the appropriate eCRF or SAE Report Form and submitted as necessary by the Investigator and/or Designee(s). Any suspected AEs related to the devices or trial procedure must be reported to the Sponsor or Designee within 24 hours of first awareness of the event.

Classification of an AE

The following guidelines will be used to describe the severity of the AE:

- Mild – Event requires minimal or no treatment and do not interfere with the subject's daily activities.
- Moderate – Event results in a low level of inconvenience or concern with the therapeutic measures. Moderate events may cause some interference with functioning.
- Severe – Event interrupts a subject's usual daily activity and may require systemic drug therapy or other intervention.
- Serious – Serious events are usually potentially life-threatening or incapacitating. Of note, the term "severe" does not necessarily equate to "serious."

Relationship of an AE

The evaluation of relatedness must consider etiologies such as natural history of the underlying disease, concurrent illness, concomitant therapy, trial-related procedures, accidents, and other external factors. In a device trial, the trial product(s) must always be suspect.

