Any adverse event associated with an FDA cleared component will be recorded as a device complaint and reported via the MDR program (21 CFR Part 803). Complaints will also be reported to the IRB in accordance with each IRB's requirements. Device complaints should be reported to the Sponsor as soon as the site becomes aware of the complaint. The Sponsor may request further information and documentation from the site when complications and/or malfunctions are observed and reported.

Recording and Reporting of Pre-Existing Conditions

Pre-existing medical conditions and symptoms due to pre-existing medical conditions, surgery or admission to ICU will not be recorded as adverse events. The admission of a critically ill patient in the intensive care unit is commonly due to one or several serious medical conditions and/or a major surgery, which may cause changes and abnormalities of blood chemistry, diagnostic and physiological parameters. In the event there is a deterioration of a pre-existing medical condition or symptoms due to the use of the Trial product(s) or a Trial related procedure, then the review of the event will be initiated, and an AE will be recorded if it meets the definition. Any events occurring prior to the exposure to the Trial product(s) or Trial related procedure will be recorded as medical history.

Reporting Adverse Events to the FDA

Confirmed UADEs will be evaluated by the Clinical Events Committee. The FDA, all participating principal investigators and their reviewing IRBs will be informed no later than 10 working days after Edwards Lifesciences or designee first becomes aware of the effect.

Reporting Adverse Events to the Responsible IRB

In accordance with applicable policies of the IRB, the Investigator will report, any observed or volunteered confirmed adverse event that is determined to be (1) unexpected; (2) related or possibly related to the research; and/or (3) involves increased or greater risk of harm to participant(s) or others than was previously known or approved by the IRB. AE reports will be submitted to the IRB in accordance with the IRB policies and procedures.

Confirmed UADEs will be evaluated, and the reviewing IRB will be informed of the results of the Trial no later than 10 working days after Edwards or when the designee first becomes aware of the effect.

Recording and Reporting AE Time Period

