3.2. Primary Safety Endpoint

Serious adverse events through 30 days as indicated below:

- Serious intraoperative and post-operative complications between each cohort
- Device-related serious adverse events (SAEs).

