6.2. Handling of Missing Data

Demographic and baseline characteristics are collected from the study subjects as part of screening. If missing data are not related to the subject's eligibility criteria, missing data will be presented by the valid sample size in the demographic and baseline characteristics summary statistics table. Subjects with missing data will be included in the final analysis. However, if the missing data are related to the subject's eligibility, this will be considered a protocol deviation, and in this case, the study data from this subject will be reviewed internally, to determine if the subject should be excluded from the final analysis set.

Algorithms for imputing the missing dates of safety events are given below. Generally, the safety event date will be assigned as the earliest possible date that is on or after the procedure date.

- If the year is unknown, then the date will be imputed using the procedure date
- If the month is unknown, then:
 - If the year matches the year of the procedure date, then impute the month and day using the procedure date
 - Otherwise, assign the procedure month
- If the day is unknown, then:
 - If the month and year match the month and year of the procedure date, then impute the day using the procedure date
 - Otherwise, assign '01'

Unless otherwise noted, no other data imputation will be made.

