9.3. Imputation for Missing Dates for Safety Events

Algorithms for imputing the missing dates of safety events are given below.

- If the year is unknown, then the date will be imputed using the procedure date
- If the month is unknown, then:
 - If the year matches the year of the procedure date, then impute the month and day using the procedure date
 - Otherwise, assign 'January'

 Edwards	Revision Date: May 7, 2024	Rev	For Use Only by Affiliates of Edwards Lifesciences	Page 20
	Title	A randomized trial of the Hypotension Prediction Index in the cardiac operating room and the intensive care unit		

- If the day is unknown, then:
 - If the month and year match the month and year of the procedure date, then impute the day using the procedure date
 - Otherwise, assign '01'

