9.4. Risk Assessments

The safety data will be summarized for all subjects in the safety population (mITT). Safety will be assessed through summarizing adverse events and judging the compliance with study treatment. The frequency and percentage of AEs and SAEs will be reported in summary tables by treatment group. Safety data will not be subjected to any imputation and will be summarized on an observed case basis. Plots showing the incidence of AEs and SAEs and their relative risk (with 95% confidence interval) will also be produced.

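### The safety endpoint is SAEs through day 30, but the final contact is allowed from day 15, so up to 15 of the 30 days can be unobserved yet counted as event-free

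*Combined protocol and SAP*

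**What the plan says.** **Endpoint.** Protocol 7 states: "The primary safety endpoint is to assess all serious intraoperative and post-operative adverse events through 30 days". SAP 3.2 has the same horizon: "Serious adverse events through 30 days as indicated below". SAP 8.2.1 compares the arms by events over subjects, x/n, and SAP 9.2 tabulates events for day 0 and days 1 to 30.

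**Follow-up.** Protocol 4 (Schema): "A 30-day follow up will take place 30 days (± 15 days) post-operation", by phone or in person. The Schedule of Events in Protocol 6 repeats the ±15 days and shows no other contact after discharge. Protocol 9 collects adverse events up to that follow-up and sets no minimum day. SAP 5.2 applies no analysis windows and offers only an optional sensitivity analysis that drops visits far out of time.

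**What is recorded.** Protocol 9 defines an adverse event as "any untoward medical occurrence in a clinical trial of a Trial Device regardless of the causal relationship". Under Pre-Existing Conditions the same chapter says that "symptoms due to pre-existing medical conditions, surgery or admission to ICU will not be recorded as adverse events".

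**Missing dates.** For an event with unknown month in a year other than the procedure year, SAP 6.2 says "Otherwise, assign the procedure month" and SAP 9.3 says "Otherwise, assign 'January". SAP 9.4 says "Safety data will not be subjected to any imputation".

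**The concern.** A 30-day proportion needs every subject in the denominator to be observed for 30 days, or a method that allows for shorter observation. The plan has neither. A call on day 15 complies fully with the protocol, so no deviation or out-of-window rule would flag it, and an event on day 20 that nobody asks about later leaves the subject in the event-free count.

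This matters because SAP 8.2.1 does more than describe safety. It plans to conclude, from a p-value below 0.025 and a negative difference, that HPI-guided care lowers complications and SAEs. Such a conclusion needs 30-day rates that are what they claim to be.

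The other two items bear on the same count. If sites cannot tell a symptom of surgery from a recordable complication, the numerator depends on local reading. If two date rules place one event on different days, its 30-day status depends on which section the programmer follows.

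**Working it through.** The documents give no expected SAE rate, sample size or power for the safety endpoint, so there is no planned figure to reproduce.

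**1. Days left unobserved**
- Inputs: horizon day 30 (Protocol 7, SAP 3.2); contact window 30 ± 15 days (Protocol 4 and 6).
- Earliest contact: 30 − 15 = day 15. Latest: 30 + 15 = day 45.
- Unobserved days for a contact on day d: max(0, 30 − d).
- Worst case, d = 15: 15 of 30 days, or 50%. For d of 30 or more: none.
- Mean if contacts were uniform over the 31 days 15 to 45 (assumption): (15 + 14 + … + 1)/31 = 120/31 = 3.87 days, and 3.87/30 = 12.9%.

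**2. From days to missed SAEs**

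Unobserved days are not missed events; that step needs SAE timing, which the documents do not give. Let s be the share of subjects contacted on day 15, the rest being contacted on day 30 or later, and f the share of SAEs with first onset on days 16 to 30. The under-count is s × f. Both inputs are assumptions, with s from 10% to 100% and f from 5% to 30%.

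| s | f | SAEs missed |
|---|---|---|
| 10% | 5% | 0.5% |
| 25% | 20% | 5% |
| 100% | 30% | 30% |

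**3. Effect on the comparison**

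The window is identical in both arms. If the under-count is too, both rates shrink by the same factor and some power is lost. Illustration, with assumed rates: 175 per arm, one-sided 0.025, control rate 30%, relative reduction 30%. Power is 48.9% with full capture, 46.3% with a 5% under-count and 38.6% with a 20% under-count.

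**4. Does the SAP repair it?**
- SAP 5.2: the optional sensitivity analysis concerns visits far out of time; day 15 is within the allowed window.
- SAP 5.1 and 6.1: a censoring day and Kaplan-Meier summaries are defined, but SAP 8.2.1 does not use them for this endpoint.

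**5. Recording rule**

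The adverse event definition ignores cause. The Pre-Existing Conditions paragraph leaves out symptoms caused by surgery or ICU admission, and reopens the question only for deterioration or symptoms attributed to trial product or a trial procedure. The endpoint is serious intraoperative and postoperative complications. No sentence says where a symptom of surgery ends and a complication begins.

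**6. Date rules**

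Example: procedure 10 December 2023, event year 2024, month and day unknown.
- SAP 6.2: 1 December 2024, day 357, outside 30 days.
- SAP 9.3: 1 January 2024, day 22, inside.

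Under SAP 9.3 an event is placed within 30 days only if 1 January is at most 30 days after the procedure. A procedure on 1 December gives day 31 and one on 2 December gives day 30. The rules therefore change 30-day status only for procedures on 2 to 31 December: 30 of 365 dates, or 8.2%, and then only with the year known and the month missing. SAP 6.2 also opens with the principle of taking the earliest date not before the procedure. January satisfies it; the procedure month does not.

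**The case against.** The strongest reply is that the target is day 30, Protocol 4 describes participation to 30 days after the procedure, most calls may come on or after day 30, and calls from day 30 lose nothing. The 13% is a share of days under an invented contact pattern. All of this stands. It limits what can be said about size, but it does not supply the missing rule that observation must reach day 30.

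Some stronger readings are tempting, and the documents do not support them:

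- **That surgery-related events are excluded from recording.** The sentence bars symptoms and does not mention complications. Protocol 4 collects intraoperative and postoperative complications, and the Medical Reviewer (Protocol 10) classifies events by relation to the procedure. This is an unreconciled ambiguity.
- **That complications are collected only to day 1.** The Schema names them only for the procedure and day 1, but the Schedule of Events records adverse events at every stage from the procedure to the 30-day contact, and Protocol 9 asks about SAEs at each visit.
- **That an unblinded causality judgement biases the arms.** Clinicians do know the allocation, and overtreatment under the HPI protocol is a possible cause in one arm only. But every subject wears the Acumen IQ sensor (Protocol 6), and nothing says that the attribution test governs serious complications. Differential capture is conceivable but not shown.
- **That the date rules under-count.** SAP 6.2 can push an event out of the window and SAP 9.3 can keep it in. The rules that both sections share, for an unknown year or an unknown month in the procedure year, move events to the procedure date. SAP 9.4 can also be read as referring to missing outcomes rather than dates.

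**Conclusion.** The window defect holds. Under the current text a subject can complete the trial on day 15 and be counted as free of SAEs to day 30, and no planned analysis corrects this. That 30-day SAEs **will** be under-counted goes too far: they **can** be, by an amount that depends on how many contacts fall before day 30 and on when SAEs occur. The documents state neither, which is why the assumed range in the working is as wide as 0.5% to 30% of SAEs. The expected result is 30-day rates that are too low in both arms, with some loss of power.

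The recording rule and the date rules are secondary. The first needs a clarifying sentence. The second is a true contradiction inside the SAP, which the SAP's precedence over other study documents cannot resolve, but its practical reach is very small. The main point is worth correcting because the change is cheap and the endpoint carries a formal test.

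**What to change.** **Main change.** In Protocol 4 (Schema) and the Schedule of Events, set the final contact to day 30 through day 45, not before day 30. In SAP 8.2.1 and 9.2, count events with onset through day 30. Unobserved days then fall from at most 15 to none for every subject who is reached. For anyone already contacted earlier, a record check to day 30 would close the gap.

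**Secondary changes.**
- Protocol 9: state that serious complications are recorded in both arms regardless of cause, and limit the Pre-Existing Conditions sentence so that it does not cover them.
- SAP 6.2: delete the procedure-month rule and keep the January rule of SAP 9.3, which follows SAP 6.2's own principle.
- SAP 9.4: say that the bar on imputation does not apply to event dates.

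**Cost.** A small protocol amendment with IRB approval and a few lines of SAP text. Some calls will come up to about two weeks later than now allowed, and sites may complete more SAE forms.

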5. SUBJECT CONSENT, SELECTION AND WITHDRAWAL

General Characteristics of the Proposed Subject Selection

Up to 350 subjects (including 5 roll-in subjects) scheduled for cardiopulmonary bypass surgery (including CABG, valve and or a combination) and receiving pressure monitoring with an arterial line, who are at least 18 years of age will be enrolled in the trial. Only subjects meeting all inclusion criteria who have provided informed consent will be enrolled. Subjects who have been screened but did not sign an informed consent form will not be considered enrolled and will not have any eCRFs (electronic Case Report Forms) completed. The subject will be considered enrolled once the Acumen IQ sensor is connected to the arterial line.

Informed Consent

Before a subject undergoes any trial procedures, an informed consent will be obtained utilizing the IRB approved consent form. All consent procedures will be conducted in a manner that is consistent with the applicable regulations and in accordance with Good Clinical Practice (GCP).

During the consent procedure, each potential subject will be given ample time to discuss participation in the trial and to have any questions or concerns addressed by the Principal Investigator or Investigator. Each subject will be provided with a copy of the IRB approved consent.

Subject Eligibility

All eligible subjects should be screened for trial eligibility. The Investigator and/or Designee(s) at the Study site shall review the candidate's eligibility. The trial site should maintain a cumulative log of all screened subjects that are eligible in participating.

Inclusion Criteria

1. Subjects who are at least 18 years of age
2. Subjects who have signed the Informed Consent Form
3. Subjects with planned pressure monitoring with an arterial line
4. Subjects with planned sternotomy
5. Subjects with planned general anesthesia
6. Subjects who have ASA Physical Status ≤ 4
7. Subjects with planned cerebral oximetry monitoring
8. Subjects with planned overnight hospitalization
9. Subjects with planned cardiopulmonary bypass (CPB) "on-pump" surgery

Exclusion Criteria

1. Subjects with a physical site area too limited for proper sensor placement
2. Subjects with contraindications for arterial line placement
3. Subjects participating in another (interventional) study
4. Subjects in whom an intraoperative MAP target will be < 65 mmHg

THIS DOCUMENT CONTAINS CONFIDENTIAL AND PROPRIETARY INFORMATION OF EDWARDS LIFESCIENCES, LLC. IT MAY NOT BE REPRODUCED OR DISCLOSED WITHOUT PRIOR WRITTEN PERMISSION FROM EDWARDS LIFESCIENCES, LLC.

Edwards Lifesciences, Edwards, the stylized E logo, HemoSphere, Acumen IQ, Swan Ganz and ForeSight Elite are trademarks of Edwards Lifesciences Corporation.

5. Subjects with pre-op or pre-pump or post-pump LVEF <15%¹
6. Subjects requiring heart transplant
7. Subjects with pre-existing circulatory support devices or planned circulatory support devices post-bypass
8. Subjects requiring emergency surgery
9. Subjects with known or identified severe PAH (defined as pulmonary systolic pressures > 70mmHg or mean pressures > 55mmHg) as determined by a pre-operative echo or intraoperative Swan-Ganz²
10. Subjects with cardiovascular instability in the operating room necessitating the need to go back on bypass for a subsequent run

¹ Pre-operative echo will take precedence over pre-pump echo. In the event of discrepancy on numbers, a final decision will be made based on a discussion between the PI and the cardiac anesthesiologist performing the pre-pump echo.

² Severe PAH is qualified as PA systolic pressure >70mmHg and/or mean pressure >55mmHg as documented on a pre-operative echo or cardiac catheterization. Or in the absence of these a sustained pressure as above after the insertion of a Swan-Ganz for at least 60 minutes in the pre-bypass period. All severe PAH pressure values should be attributed to an irreversible etiology in the best clinical judgement of the treating team to meet exclusion criteria.

THIS DOCUMENT CONTAINS CONFIDENTIAL AND PROPRIETARY INFORMATION OF EDWARDS LIFESCIENCES, LLC. IT MAY NOT BE REPRODUCED OR DISCLOSED WITHOUT PRIOR WRITTEN PERMISSION FROM EDWARDS LIFESCIENCES, LLC.

Edwards Lifesciences, Edwards, the stylized E logo, HemoSphere, Acumen IQ, Swan Ganz and ForeSight Elite are trademarks of Edwards Lifesciences Corporation.

HPI CARE Trial
Protocol #: 2020-19

Screen Failures [or Late Screen Failures]

Screen failures are defined as participants who consent to participate in the clinical trial but are not subsequently randomly assigned to the trial intervention or entered in the trial. A minimal set of screen failure information is required to ensure transparent reporting of screen failure participants, to meet the Consolidated Standards of Reporting Trials (CONSORT) publishing requirements and to respond to queries from regulatory authorities. Minimal information includes demography, screen failure details, and eligibility criteria.

Enrolled Subjects

A subject will be considered enrolled in the trial once the subject has signed the informed consent, has been assigned a Study Identification Number (Study ID), an arterial line has been placed and Acumen IQ sensor has been connected. The Study ID will be an 874-XXX (6-digit) number; the first three numbers will identify the site, and the second set of numbers will identify the subject identification number. Roll-in cases will be assigned a unique Study ID and be analyzed separately from the pivotal cohort. There will be an identification number assigned to each investigator. The ID for each subject will remain the same throughout enrollment at each site.

Roll-in Subjects

In order to avoid a learning curve bias, up to five (5) Roll-in cases may be performed per site. Roll-in cases will be assigned a unique Study ID and will be analyzed separately from the Pivotal cohort. There will be an identification number assigned to each investigator. The ID for each investigator will remain the same throughout enrollment at each site.

Early Withdrawal of Subjects

Subjects may voluntarily withdraw consent at any time during the trial with no loss of benefit or penalty. The Investigator may withdraw any subject if they determine that continued participation in the trial may be detrimental to the subject's safety and welfare. Subjects withdrawn due to a device complaint or adverse event will be followed through the 30-day follow-up. In addition, if the procedure is aborted early, but after the subject is exposed to trial product, the subject will be followed for 30 days after the aborted procedure. Each subject withdrawal will be documented on the appropriate eCRF.

Lost to Follow-Up

A participant will be considered lost to follow-up if he or she fails to return the 30-day follow-up phone call after 3 attempts and is unable to be contacted by the trial site staff.

The following actions must be taken if a participant fails to return to the clinic for a required trial visit:

- The site will attempt to contact the participant and reschedule the missed visit and counsel the participant on the importance of maintaining the assigned visit schedule and ascertain if the participant wishes to and/or should continue in the trial.
- Before a participant is deemed lost to follow-up, the investigator or designee will make every effort to regain contact with the participant (where possible, 3 telephone calls and, if necessary, a certified letter to the participant's last known mailing address or local equivalent methods). These contact attempts should be documented in the participant's medical record or trial file.
- Should the participant continue to be unreachable, he or she will be considered to have withdrawn from the trial with a primary reason of lost to follow-up.

